| RECIST | Response Evaluation Criteria in Solid Tumors |
| SAE | Serious Adverse Event |
| SAbr | Stereotactic ablative body radiotherapy |
| SBRT | Stereotactic body radiotherapy |
| SCCC | Simmons Comprehensive Cancer Center |
| scRNAseq | Single cell RNA sequencing |
| SGOT | Serum Glutamic Oxaloacetic Transaminase |
| SPGT | Serum Glutamic Pyruvic Transaminase |
| TRUS | Transrectal ultrasound |
| WBC | White Blood Cells |

STUDY SCHEMA**Primary Endpoint & Hypothesis**

- Percentage of Children Ages 3-7 Requiring General Anesthesia: We hypothesize that PROMISE will lead to a reduction in the percentage of patients **ages 3-7** who require general anesthesia during radiation treatment from **70%** (institutional historical control) to **30%**.

Secondary Endpoints

Secondary endpoints will be analyzed for those on trial treated with PROMISE vs. anesthesia.

- Patient/family-reported health quality of life (PedsQL 3.0 Cancer Module) and anxiety (mYPAS-SF).
- Workflow data: treatment time, average patient movement, and number of beam turn offs due to movement beyond threshold.
- Overall cost of treatment.

STUDY SUMMARY

| | |
|--|--|
| Title | Pediatric Radiation Oncology with Movie Induced Sedation Effect (PROMISE): A Phase II Clinical Trial to Safely Reduce Anesthesia Use |
| Short Title | PROMISE Clinical Trial to Reduce Anesthesia Use |
| Protocol Number | STU-2021-1005 |
| Phase | Phase II |
| Methodology | Single-arm, open label |
| Study Duration | 2 years |
| Study Center(s) | Single-center |
| Objectives | 
Primary: To decrease the total number of pediatric patients who require general anesthesia through the use of PROMISE.
 
Secondary:
 
 - To assess the impact that PROMISE has on patient/family anxiety and quality of life, treatment time and clinical efficiency, and overall cost. - To determine the average patient movement and beam stoppages with the use of PROMISE. |
| Number of Subjects | 30 |
| Diagnosis and Main Inclusion Criteria | Age 3-11 and planned to undergo radiation therapy. |
| Study Product(s), Dose, Route, Regimen | PROMISE: an audio/visual technology for children to focus on during each radiation treatment to prevent movement. |
| Duration of administration | PROMISE will be used for each fraction of radiation treatment; number of fractions will vary by patient depending on individual diagnosis and treatment plan. |

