| Reference therapy | Institutional historical control of percentage of patients age 3-7 who required general anesthesia during radiation therapy. |
| Statistical Methodology | 
We hypothesize that PROMISE will lead to a reduction in the percentage of patients ages 3-7 who require general anesthesia use from 70% (historical control) to 30%. Using a two-sided exact binomial test with a significance level of 0.05 and power=80%, a sample size of 13 patients (ages 3-7) will be needed to detect this difference.
 
In our past experience, ~42% of children ages 3-11 (eligibility criteria) are between 3-7 years old, so 30 children total will be needed to enroll 13 who are between 3-7 years old.
 |

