Daily rounds of general anesthesia can easily double the amount of time patient, parents, and medical staff (including anesthesiologists) spend in the hospital for administration and recuperation, making the process less efficient and increasingly expensive. For example, anesthesia costs average \$50,000 per child over a typical six week treatment, therefore a reliable alternative to general anesthesia would drastically and immediately decrease costs²³. Logistically, involvement of anesthesia is difficult. Radiation oncology suites are often stand-alone structures not located near or in major hospitals or academic centers, where anesthesia is more easily provided⁶. Because anesthesiologists are not normally on site in a radiation oncology suite, it creates obstacles in scheduling, transportation, and compensation. This problem is likely to worsen moving forward because radiation oncology suites are more frequently being built further from, not closer to, major hospitals or academic centers²⁴. Anesthesia care provided in pediatric radiation therapy oncology suite is also often less efficient and safe. Anesthesiologist may be accustomed to working in operating room suites, which compared to radiation oncology suites, are relatively more efficient and have safer facilities, equipment, and personnel²⁴. One such example is an anesthesiologist is not allowed in the radiation suite during treatment, which is not the case in a typical operating room^{3,6}.

Current Attempts to Minimize Anesthesia in Pediatric Oncology

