Multiple options are being explored to minimize the use of anesthesia in pediatric radiation oncology with varying levels of success: music therapy plays music pre-selected by the patient during treatment^{3,25}; interactive intervention and psychoeducational therapy entails preparatory play therapy, interactive support, and behavioral modeling^{3,26-28}; psychological preparation prepares patients emotionally and mentally for the upcoming treatments^{3,29}. Electronic monitors working in concert with behavioral training display movies or cartoons to distract patients during treatment used to increase patient cooperation and avoid anesthesia^{3,28}. AVATAR, a similar device to PROMISE created by Stanford, has shown promising results. Stanford's study, published online January 11, 2020 reviewed 224 pediatric patients three years before and three years after AVATAR implementation. They found that more patients avoided general anesthesia for all ages; 73.2% before AVATAR implementation versus 63.4% after implementation. AVATAR use also demonstrated a reduction in treatment time per session by 38% and 326 fewer anesthesia sessions over a three year period, a total cost savings of roughly \$500,000³⁰.

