2.2 Secondary Objectives

- 2.2.1 To assess the impact that PROMISE has on patient/family anxiety and quality of life, treatment time and clinical efficiency, and overall cost.
- 2.2.2 To determine the average patient movement and beam stoppages with PROMISE.

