2.3 Endpoints

- 2.3.1 Primary: The percentage of pediatric patients age 3-7 who require daily general anesthesia for all treatments, compared to historical control. (Correlates with Primary Objective 2.1.1)
- 2.3.2 Secondary: Secondary outcomes will be measured comparing those who successfully are treated using PROMISE for any fraction vs. those who require general anesthesia for all fractions. (Correlates with Secondary Objective 2.2.1)
 - Patient/family-reported health quality of life, assessed using PedsQL 3.0 Cancer Module.
 - Patient anxiety, measured by the modified Yale Preoperative Anxiety Survey Short Form (mYPAS-SF).
- 2.3.3 Exploratory: Exploratory outcomes will also be measured comparing those who successfully are treated using PROMISE for any fraction vs. those who require general anesthesia for all fractions. (Correlates with Secondary Objectives 2.2.1 and 2.2.2).
 - Treatment time per fraction.
 - Workflow data: treatment time, average patient movement (magnitude, vertical, longitudinal, lateral, yaw, roll, and pitch), the number beam turn offs due to movement beyond threshold and total time out of tolerance.
 - Cost savings.

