9.2 Sample Size and Accrual

In order to detect a reduction in the rate of general anesthesia use in pediatric patients age 3-7 from the historical control of 70% to the hypothesized 30%, the total number of patients needed to achieve 84% power is 13, using a two-sided exact binomial test with a significance level of 0.05. Over the last two years (2018-2019) at the University of Texas Southwestern we treated 52 pediatric patients aged 3-11 who would be eligible for this study, so on average 26 patients/year. We estimate the ability to enroll the large majority (>80%) of patients who are eligible for this trial, and so we estimate enrolling 20 patients per year. Of these patients, ~42% are ages 3-7, so we estimate that 8-9 patients in our 3-7 age target range per year will be enrolled. Thus, we expect to enroll a total of 30 patients, of whom 13 will be ages 3-7, in ~1.5 years, with the total trial completed in ~2 years.

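### Cost savings are measured against children anesthetized at every fraction, so the endpoint prices an anesthesia course instead of the saving due to PROMISE

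*Combined protocol and SAP*

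**What the plan says.** Objective 2.2.1 is "To assess the impact that PROMISE has on patient/family anxiety and quality of life, treatment time and clinical efficiency, and overall cost". Section 2.3.3 then lists cost savings among outcomes governed by one contrast between two groups of trial children: "Exploratory outcomes will also be measured comparing those who successfully are treated using PROMISE for any fraction vs. those who require general anesthesia for all" of them. The Study Schema uses the same on-trial contrast, and there overall cost of treatment is a secondary endpoint: "Secondary endpoints will be analyzed for those on trial treated with PROMISE vs. anesthesia".

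The historical control is attached only to the primary endpoint, which 2.3.1 defines as "The percentage of pediatric patients age 3-7 who require daily general anesthesia for all treatments, compared to historical control". The Study Summary gives the reference as "Institutional historical control of percentage of patients age 3-7 who required general anesthesia during radiation therapy". Section 9.2 supplies the rates: "from the historical control of 70% to the hypothesized 30" percent.

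Section 9 contains no cost method, cost components, price source or usual-practice cost baseline. The only cost figures are background in Section 1.2: "anesthesia costs average \$50,000 per child over a typical six week treatment", and, for a similar audiovisual device compared before and after its introduction, "326 fewer anesthesia sessions over a three year period, a total cost savings of roughly" $500,000.

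**The concern.** A saving caused by PROMISE is the cost of treating these children as they would otherwise have been treated, minus the cost of treating them with PROMISE available. Without PROMISE, about 30% of children aged 3-7 would have had no anesthesia. The comparator in 2.3.3 has no such children.

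Suppose PROMISE prevented nothing. The 30% who avoid anesthesia anyway, and any older children who do, would still be classed as treated with PROMISE and compared with children anesthetized at every fraction. The difference would be large although no course had been averted. Adjustment for age or baseline condition does not cure this, because perfectly matched groups would still differ by the cost of anesthesia. A trial that missed its primary endpoint could therefore report a substantial saving per child.

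**Working it through.** **The plan's own figure.** The documents state no expected value for the cost endpoint. The one stated calculation using the same 70% and 30% is the power in 9.2. With 13 children, rejecting when 5 or fewer need anesthesia has lower-tail probability 0.0182 at 70% and power 0.835 at 30%, in line with the stated 84%. The inputs are therefore read as intended.

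**Inputs.**
- C, anesthesia cost per full course: $50,000 for six weeks (1.2).
- Course length: 25 to 30 fractions (1.1).
- Anesthesia rate at ages 3-7: 70% historically, 30% hypothesized (9.2).
- Enrolment: 30, about 42% aged 3-7 (9.2). That is 30 x 0.42 = 12.6 aged 3-7 and 17.4 aged 8-11.
- q: share of children anesthetized throughout on trial.
- s: share of fractions without anesthesia among PROMISE children.

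**Contrast as written.** Mean anesthesia cost is C in the anesthesia group and C x (1 - s) in the PROMISE group. The difference is C x s, and q does not appear. With s = 1 it is $50,000 per PROMISE child at q = 70% and at q = 30%.

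**Range for that amount.**
- At $50,000 / 30 = $1,667 per session, 25 to 30 fractions cost $41,667 to $50,000.
- At the similar device's $500,000 / 326 = $1,534 per session, they cost $38,344 to $46,012.
- With mixed courses and C = $50,000, the contrast is $45,000 at s = 0.9 and $25,000 at s = 0.5.

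**Against usual practice, ages 3-7, s = 1.** The saving per child is C x (0.70 - q), before charging any cost of PROMISE itself:

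| q | Contrast in 2.3.3, per PROMISE child | Saving against usual practice, per child aged 3-7 |
|---|---|---|
| 70% | $50,000 | $0 |
| 50% | $50,000 | $10,000 |
| 30% | $50,000 | $20,000 |

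Mixed courses lower both figures. If historically anesthetized children had anesthesia at every fraction (assumption), the saving at q = 30% is C x (0.70 - [0.30 + 0.70 x (1 - s)]). That gives $16,500 at s = 0.9 and $2,500 at s = 0.5.

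**Totals on a common denominator, q = 30%, s = 1, C = $50,000.** The table's columns are per different groups of children, so the overstatement is taken from totals.
- Ages 3-7: credited 12.6 x 0.70 x $50,000 = $441,000; averted 12.6 x 0.40 x $50,000 = $252,000. Ratio 1.75.
- All ages, assuming every child aged 8-11 succeeds with PROMISE: credited (8.82 + 17.4) x $50,000 = $1,311,000. If none aged 8-11 was anesthetized historically, the saving is still $252,000. Ratio 5.2.
- If a share h of ages 8-11 was anesthetized historically and PROMISE removes all of it (assumption), add 17.4 x h x $50,000:
  - h = 10%: saving $339,000, ratio 3.9.
  - h = 20%: saving $426,000, ratio 3.1.
  - h = 30%: saving $513,000, ratio 2.6.

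**No-effect case at ages 3-7.** Credited 12.6 x 0.30 x $50,000 = $189,000; averted $0.

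**The case against.** The strongest reply is that this is one exploratory item in 2.3.3, with no test, power or decision rule, and that the documents never fix the cost measure. Much of that stands, and it limits what can be claimed.

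- A reader might infer that the trial would report exactly $50,000 per child even with no effect. That requires an anesthesia-only cost measure, six weeks for every child and no anesthetized fractions in the PROMISE group. The schema speaks of overall treatment cost, the number of fractions varies by patient, and the any-fraction rule admits mixed courses, which 4.1 and 5.2.2 can produce. The amount is uncertain; its independence from the number of courses prevented is not.
- A reader might divide $50,000 by $20,000 and call the contrast 2.5 times too large, or divide by $8,400 per enrolled child (0.42 x $20,000) and call it 6 times. Those quotients set a figure per PROMISE child against one per child including failures. Like for like, they are 1.75 and 5.2.
- A reader might infer that standby and long slots fall on the anesthesia group and inflate the saving. Under 4.1 and 5.2.2 standby is planned for every child at simulation and first treatment, and a child who fails first and later succeeds is a PROMISE child. Only additional failed attempts differ, and their net effect cannot be determined.
- A reader might assume that most children aged 8-11 would avoid anesthesia under usual care. Section 1.1 says only that some children up to age 12 need it, so the all-ages ratios remain conditional.

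A historical comparison is also imprecise. Assume the 70% comes from about 52 x 0.42 = 22 children treated in 2018-2019. With 13 on trial, the 40-point difference has standard error sqrt(0.21/22 + 0.21/13) = 0.160, hence a 95% interval of about 9 to 71 points, or roughly $4,000 to $36,000 per child. That is a reason to report an interval. It does not make the present comparator suitable.

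**Conclusion.** The concern holds: the comparator is wrong for the question. Followed as written, 2.3.3 returns approximately the cost of an anesthesia course (about $38,000 to $50,000 for 25 to 30 fractions, less with mixed courses) and does not move with the number of courses PROMISE prevents. The quantity in objective 2.2.1 is, at ages 3-7, $0 if anesthesia stays at 70% and about $20,000 per child if it falls to 30%.

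The 1.75-fold overstatement at ages 3-7 rests on the plan's rates and unmixed PROMISE courses; C cancels. The all-ages range of 5.2 down to 2.6 rests further on an assumed historical rate of 0 to 30% at ages 8-11 and on every child of that age succeeding.

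A reader might infer that the trial's main result is compromised. It is not: the primary endpoint already uses the historical control, and its sample size is untouched. The change should be made because cost is a stated objective and the result would be reported under the name of a saving.

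**What to change.** In 2.3.3 and the Study Schema:

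1. Define cost savings at ages 3-7 against the institutional historical control, using all enrolled children of that age including PROMISE failures: (historical minus on-trial anesthesia use) x anesthesia cost, with a confidence interval.
2. Count on-trial anesthesia by sessions, so that mixed courses are not scored as fully averted. If historical use is known only as a proportion of children, state what is assumed about their sessions.
3. Subtract the cost of standby, longer slots and failed attempts in every child. Name the cost components and price source.
4. Report ages 8-11 separately, and claim a saving there only if their historical anesthesia rate can be obtained from the 2018-2019 cohort.
5. Keep the PROMISE versus anesthesia contrast as a descriptive cost difference between children treated with and without anesthesia, not as cost savings.
6. Reconcile the status of cost, which is secondary in the schema and exploratory in 2.3.3.

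This costs protocol wording and a count of anesthesia use by age among the 52 children in 9.2. The documents do not say whether that count, or historical session counts, are available. No new patients, visits or procedures are needed. The downside is a smaller and less precise reported saving that relies on a small historical cohort.

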3.0 Subject ELIGIBILITY

Eligibility waivers are not permitted. Subjects must meet all of the inclusion and exclusion criteria to be registered to the study. Study treatment may not begin until a subject is registered.

3.1 Inclusion Criteria

- 3.1.1 Planned to undergo radiation treatment
- 3.1.2 Age 3-11 years
- 3.1.3 Eastern Cooperative Oncology Group (ECOG) performance status ≤ 2 at screening (See Section 12.1, Appendix A).
- 3.1.4 Parents or guardians with the ability to understand and the willingness to sign a written informed consent.

3.2 Exclusion Criteria

- 3.2.1 Subjects with documented medical behavior conditions or other conditions necessitating anesthesia use
- 3.2.2 Uncontrolled intercurrent illness including, but not limited to, ongoing or active infection, symptomatic congestive heart failure, unstable angina pectoris, cardiac arrhythmia, or psychiatric illness/social situations that, in the opinion of the investigator, would limit compliance with study requirements.

3.2.3 Subjects whose parents opt to not include them (the subject) in the clinical trial.

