2.0 STUDY OBJECTIVES

Hypothesis: We hypothesize that PROMISE will lead to a reduction in the percentage of pediatric patients ages 3-7 who require general anesthesia use for daily radiation treatment from 70% (historical control) to 30%.

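### The 70% null is not stated to match the trial's eligibility rules or event definition, and it is used as exactly known, so the error rate holds only if the true eligible rate is close to 70%

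*Combined protocol and SAP*

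**What the plan says.** The Study Summary describes the reference as "Institutional historical control of percentage of patients age 3-7 who required general anesthesia during radiation therapy". Section 9.2 sizes the trial to detect a fall "from the historical control of 70% to the hypothesized 30" percent, "using a two-sided exact binomial test with a significance level of 0.05", and states that "the total number of patients needed to achieve 84% power is 13". The Study Summary gives 80% power for the same 13 children.

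Two restrictions apply to trial patients. Criterion 3.2.1 excludes "Subjects with documented medical behavior conditions or other conditions necessitating anesthesia use". Endpoint 2.3.1 counts a child as an event only if daily general anesthesia is needed for all treatments.

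Neither restriction is mentioned for the control. Nowhere is the 70% given a numerator, denominator, calendar period or confidence interval. The one institutional cohort described is in 9.2, for accrual: in 2018-2019 "we treated 52 pediatric patients aged 3-11 who would be eligible for this study", about 42% of them aged 3-7. Section 9.2 does not say that the 70% comes from these children. Section 9.3 describes interim reports only, with no sensitivity analysis for the null rate.

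**The concern.** With no concurrent control, the 70% is the only comparator, and the primary conclusion is only as sound as that figure.

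Two differences in description matter, and both would act in the direction of success.

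- **Eligibility.** A child whose condition makes anesthesia necessary would count as an event in an unfiltered control but cannot enter the trial. Removing such children from one side only lowers the trial rate even if PROMISE does nothing.
- **Event definition.** A historical child anesthetized for part of the course fits the Study Summary's description of the control. A trial child with the same course is not an event under 2.3.1.

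A third issue is precision. A one-sample exact test takes the null as a constant, so any sampling error in the 70% is left out of the p-value. At stake is a claim of success that partly reflects how the control was assembled.

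**Working it through.** **Inputs.** Null 0.70, alternative 0.30, n = 13, two-sided exact binomial test at 0.05 (9.2). X is the number of the 13 children who need anesthesia.

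**Step 1: the plan's own figure.**
- P(X ≤ 5 | 0.70) = 0.0182 and P(X ≤ 6 | 0.70) = 0.0624. With 0.025 in the lower tail, success means X ≤ 5.
- The upper region is X = 13, with probability 0.70^13 = 0.0097. Attained two-sided size = 0.0182 + 0.0097 = 0.0279.
- Power = P(X ≤ 5 | 0.30) = 0.8346, which agrees with the stated 84% to within a point.

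**Step 2: the same rule at other no-effect rates.** Let p be the true rate in eligible children, on the trial's event definition, without PROMISE. Lower tail = P(X ≤ 5 | p); both tails adds p^13.

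To translate p into a share excluded, assume that a fraction f of the historical 3-7-year-olds would have been removed by 3.2.1 and that all of them had anesthesia. Then p = (0.70 − f)/(1 − f). The documents give no value for f, so a range is shown.

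| f (assumed) | p | lower tail | both tails |
|---|---|---|---|
| 0 | 0.700 | 1.8% | 2.8% |
| 5% | 0.684 | 2.5% | 3.2% |
| 10% | 0.667 | 3.5% | 4.0% |
| 15% | 0.647 | 4.9% | 5.2% |
| 20% | 0.625 | 6.9% | 7.1% |
| 25% | 0.600 | 9.8% | 9.9% |
| 30% | 0.571 | 14.0% | 14.1% |

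The lower tail reaches 2.5% at p = 0.684 (f about 5%). The two-sided error reaches 5% at p = 0.650 (f about 14%).

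**Step 3: what a bare success excludes.** This needs no assumption about f. The exact 95% upper limit for 5/13 is 68.4%. A trial that just succeeds therefore rules out control rates of 68.4% and above and no lower ones, which leaves a margin of 70 − 68.4 = 1.6 percentage points for error in the null.

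**Step 4: a separate, alternative assumption.** Suppose the 70% came from the 2018-2019 cohort. Then 0.42 × 52 = 21.8, or about 22 children aged 3-7, described as eligible. The exclusion bias then eases, but the rate is imprecise: 15/22 (68%) has an exact 95% interval of 45% to 86%, and 16/22 (73%) has 50% to 89%. Steps 2 and 4 assume different sources for the 70%, so their effects should not be added.

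**Step 5: consequence of a lower null at n = 13.**
- Null 0.625: P(X ≤ 4) = 0.021 and P(X ≤ 5) = 0.069, so the boundary is 4 or fewer. Power at 0.30 is 65%.
- Null 0.571: P(X ≤ 3) = 0.014 and P(X ≤ 4) = 0.051, so the boundary is 3 or fewer. Power at 0.30 is 42%.

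**The case against.** The documents are silent on whether the 70% was filtered; they do not say that it was not. The description of the control is one line in a summary table, and the only institutional cohort described is called eligible. A reader might infer that the control definitely includes children whom 3.2.1 would exclude. The text does not support that.

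A reader might also infer that the false-positive rate is higher than stated. That is conditional. Because the exact test is conservative at n = 13, it uses only 2.8% of its 5% at a true 70%. An excluded share of up to about 14% still keeps the two-sided error within 5%. The calculation also takes the extreme case in which every excluded child had anesthesia. If the true eligible rate is above 70%, the lower-tail error is smaller than 1.8%.

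A fixed null is inherent in a single-arm phase II design, which the protocol declares openly. A two-sample comparison is an addition, and its result depends on the assumed count: for 5/13, Fisher's test gives p = 0.16 against 15/22, 0.075 against 16/22 and 0.031 against 70/100. No single one of these should be presented as the effect of ignoring the uncertainty.

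All of this stands, and it limits the claim. It does not supply the missing source, count, interval, eligibility filter or event definition. It also leaves unresolved that 2.3.1 and the Study Summary describe the event differently.

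**Conclusion.** The concern holds in conditional form. The 70% is not stated to be restricted to children who would pass 3.1-3.2 or to use the 2.3.1 event, and it is treated as exact. If either mismatch is present, it favors a finding of success.

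The stated error rate is safe if the true eligible rate is 70% or close to it. The lower tail exceeds 2.5% below about 68.4%, and the two-sided error exceeds 5% below about 65%. The corresponding excluded shares, about 5% and 14%, rest on the assumption that all excluded children had anesthesia. No size is put on the event-definition mismatch, because the documents give nothing to size it with.

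If the 70% instead came from about 22 eligible children, the main problem becomes imprecision, with an interval of about 45% to 86%. The documents do not show which situation applies. In either case, a result near the boundary cannot be interpreted until the control is documented.

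**What to change.** 1. Recompute the control rate from the institution's charts in children aged 3-7 who would pass 3.1-3.2, counting events as in 2.3.1.
2. State its period, n/N and exact 95% interval in 9.2. Use that rate as the null and restate the success boundary and the power at n = 13.
3. Plan to report the trial rate with its exact 95% interval, explaining that the upper limit is the lowest control rate the result excludes.
4. Show how the conclusion changes over a range of null rates. An exact two-sample comparison with the chart cohort can be added as an optional sensitivity analysis.

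The cost is a review of the institution's own charts (about 22 children if the 2018-2019 cohort is used) plus revised wording. The downside is that a lower null reduces the stated power at n = 13, to 65% at a null of 0.625 and 42% at 0.571. That lower power should be stated; enrolling more children is not part of this change.
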